## **9.6 Good Clinical Practice**

The procedures set out in this study protocol are designed to ensure that the Sponsor and Investigator abide by the principles of the GCP guidelines of the ICH, and of the Declaration of Helsinki (2013). The study also will be carried out in keeping with local legal requirements.

## **9.7 Informed Consent**

Before each subject is admitted to the study, informed consent will be obtained from the subject (or his/her legally authorized representative) according to the regulatory and legal requirements of the participating country. This consent form must be dated and retained by the Investigator as part of the study records. The Investigator will not undertake any investigation specifically required only for the clinical study until valid consent has been obtained. The terms of the consent and when it was obtained must also be documented in the EDC system.

If a protocol amendment is required, the ICF may need to be revised to reflect the changes to the protocol. If the consent form is revised, it must be reviewed and approved by the appropriate IEC/IRB, and signed by all subjects subsequently enrolled in the study as well as those currently enrolled in the study.

## **9.8 Protocol Approval and Amendment**

Before the start of the study, the study protocol and/or other relevant documents will be approved by the IEC/IRB/Competent Authorities, in accordance with local legal requirements. The Sponsor must ensure that all ethical and legal requirements have been met before the first subject is enrolled in the study.

This protocol is to be followed exactly. To alter the protocol, amendments must be written, receive approval from the appropriate personnel, and receive IRB/IEC/Competent Authority approval prior to implementation (if appropriate).

Administrative changes (not affecting the subject benefit/risk ratio) may be made without the need for a formal amendment. All amendments will be distributed to all protocol recipients, with appropriate instructions.

## **9.9 Duration of the Study**

For an individual subject, the maximum duration of the study for each subject will be:

- Part A (SAD): up to 42 days (including up to 28 days for Screening, up to 7 days treatment and up to 7 days Follow-up).

- Part B (MAD): up to 42 days (including up to 28 days for Screening, up to 8 days treatment and up to 6 days Follow-up).

The study will close when all subjects have completed the Final Follow-up Visit.

## **9.10 Premature Termination of the Study**

If the PI and the Sponsor becomes aware of conditions or events that suggest a possible hazard to subjects if the study continues, the study may be terminated after appropriate consultation between the relevant parties. The study may also be terminated early at the Sponsor's discretion in the absence of such a finding.

Conditions that may warrant termination include, but are not limited to:

- The discovery of an unexpected, significant, or unacceptable risk to the subjects enrolled in the study;
- Failure to enroll subjects at an acceptable rate;
- A decision on the part of the Sponsor to suspend or discontinue development of the drug.

## **9.11 Confidentiality**

All study findings and documents will be regarded as confidential. The Investigator and members of his/her research team must not disclose such information without prior written approval from the Sponsor.

The anonymity of participating subjects must be maintained. Subjects will be identified on EDC system and other documents submitted to PAREXEL by their subject number. Documents not to be submitted to PAREXEL that identify the subject (e.g., the signed informed consent) must be maintained in confidence by the Investigator.

## **9.12 Other Ethical and Regulatory Issues (Optional)**

If a significant safety issue is identified, either from an individual case report or review of aggregate data, then the Sponsor will issue prompt notification to all parties – Regulatory Authorities, Investigators, and IRB/IECs.

A significant safety issue is one that has a significant impact on the course of the clinical study or program (including the potential for suspension of the development program or amendments to protocols) or warrants immediate update of informed consent.

## **9.13 Liability and Insurance**

The Sponsor will take out reasonable third-party liability insurance cover in accordance with all local legal requirements. The civil liability of the Investigator, the persons instructed by him or her and the hospital, practice, or institute in which they are employed and the liability of the Sponsor with respect to financial loss due to personal injury and other damage that may arise as a result of the carrying out of this study are governed by the applicable law.

The Sponsor will arrange for subjects participating in this study to be insured against financial loss due to personal injury caused by the pharmaceutical products being tested or by medical steps taken in the course of the study.

#### **9.14 Publication Policy**

By signing the study protocol, the Investigator agrees with the use of results of the study for the purposes of national and international registration, publication and information for medical and pharmaceutical professionals. If necessary, Regulatory Authorities will be notified of the Investigator's name, address, qualifications and extent of involvement.

An Investigator shall not publish any data (poster, abstract, paper, etc.) without having consulted with the Sponsor in advance. Details are provided in a separate document.

Page 7 of 61

PAREXEL International
Statistical Analysis Plan

ABBREVIATION AND ACRONYM LIST

Abbreviation / Acronym	Definition / Expansion
AE	Adverse event
ATC	Anatomical therapeutic chemical
AUC	Area under the concentration-time curve
AUC _(0-inf)	AUC from time zero extrapolated to infinity
AUClast	AUC from time zero to the last quantifiable concentration
BLQ	Below the lower limit of quantification
BMI	Body Mass Index
Bpm	Beats per minute
CI	Confidence interval
CL/F	Apparent clearance following oral administration
CSF	Cerebrospinal Fluid
CSP	Clinical Study Protocol
CSSRS	Columbia Suicide Severity Rating Scale
Cmax	Maximum observed concentration
Cmin	Minimum observed concentration in the dosing interval
CS	Clinically significant
C _{trough}	Concentration immediately prior to dosing
CV	Coefficient of variation
DBP	Diastolic blood pressure
ECG	Electrocardiogram
HBsAg	Hepatitis B surface antigen
HCV	Hepatitis C virus
HIV	Human immunodeficiency virus
HR	Heart rate
IMP	Investigational Medicinal Product
K-WAIS-IV	Korean Wechsler Adult Intelligence Scale-IV
LLOQ	Lower limit of quantification

PAREXEL International
Statistical Analysis Plan

Abbreviation / Acronym	Definition / Expansion
MAD	Multiple ascending dose
MedDRA	Medical Dictionary for Regulatory Activities
NCS	Not clinically significant
NK	Not known
PD	Pharmacodynamic
PDAS	Pharmacodynamic analysis set
PK	Pharmacokinetic
PKAS	Pharmacokinetic analysis set
POMS	Profile of Mood States
R _{ac}	Accumulation ratio
SAD	Single ascending dose
SAE	Serious adverse event
SAP	Statistical Analysis Plan
SBP	Systolic blood pressure
SD	Standard deviation or single dose
SE	Standard error of the mean
SOC	System Organ Class
t _½	Apparent terminal elimination half-life
t _{last}	Time of last quantifiable concentration
TEAE	Treatment-emergent adverse event
t _{max}	Time corresponding to occurrence of C _{max}
VAS	Visual Analogue Scale
V _{z/F}	Apparent volume of distribution during terminal phase
WHO-DD	World Health Organisation - Drug Dictionary
λ _z	Terminal elimination rate constant
%AUC _{ex}	Percentage of AUC _(0-inf) obtained by extrapolation

PAREXEL International
Statistical Analysis Plan

STATISTICAL ANALYSIS PLAN

The Statistical Analysis Plan (SAP) details the statistical methodology to be used in analyzing study data and outlines the statistical programming specifications for the Tables, Listings and Figures (TLFs). It describes the variables and populations, anticipated data transformations and manipulations and other details of the analyses not provided in the Clinical Study Protocol (CSP).

The analyses described are based on the final CSP 5.0, dated, 13/Feb/2017. The SAP will be finalized prior to database lock and describes the statistical analysis as it is foreseen when the study is being planned. If circumstances should arise during the study rendering this analysis inappropriate, or if improved methods of analysis should arise, updates to the analyses may be made. Any deviations from the SAP after database lock, reasons for such deviations and all alternative or additional statistical analyses that may be performed, will be described in a SAP Addendum.

PAREXEL International
Statistical Analysis Plan

1. STUDY OBJECTIVES

1.1 Primary Objective

- To evaluate the safety and tolerability of single and multiple ascending oral doses of KM-819 in healthy young adult male subjects.

1.2 Secondary Objective

- To evaluate the pharmacokinetics (PK) and pharmacodynamics (PD) of single and multiple ascending oral doses of KM-819 in healthy young adult male subjects.
- To evaluate the safety and tolerability of single and multiple oral doses of KM-819 in elderly male or post-menopausal female subjects.
- To evaluate the PK and PD of single and multiple oral doses of KM-819 in elderly male or post-menopausal female subjects.

2. STUDY DESIGN

This is a first-in-human, single-center, randomized, placebo-controlled, double-blind, sequential group Phase 1 study in healthy subjects. The aim of this study is to evaluate the safety, tolerability, PK, and PD following the escalation of single and multiple doses of KM-819. The study will consist of 2 parts (Part A and Part B).

Part A Single Ascending Dose (SAD):

This part includes up to 5 cohorts of healthy young adult male subjects receiving single ascending doses (SAD)s of KM-819, and 1 additional single-dose cohort of elderly male or post-menopausal female subjects.

Up to 40 healthy young adult male subjects and 8 healthy elderly male or post-menopausal female subjects will be enrolled and randomized to receive either KM-819 or placebo.

Each of the 5 dose escalation cohorts consists of 8 healthy young adult male subjects; 6 subjects will receive single dose of 10 mg (1 x 10 mg tablet), 30 mg (2 x 10 mg tablet),, 100 mg (1 x 100 mg tablet),,

Kainos Medicine, Inc.

Final 1.0

KMCP-819-K101

14/Nov/2017

PAREXEL International
Statistical Analysis Plan

200 mg (2 x 100 mg tablet),, or 400 mg (4 x 100 mg tablet) KM-819 and 2 subjects will receive placebo.

Cohorts will be dosed sequentially with escalating doses, escalation to the next dose level will take place only after the safety, tolerability data, and available PK data from the previously treated dose cohort has been reviewed; see Section 3.4 of CSP for dose escalation criteria. In each of the 5 single dose cohorts, dosing of subjects will be sentinel, i.e., 2 subjects will be dosed on the first day (1 subject will receive active treatment and 1 subject will receive placebo) and the remaining 6 subjects will be dosed at least 24 hours after the first 2 subjects

After completion of the 5 dose escalation cohorts, 8 elderly male or post-menopausal female subjects will be enrolled into an additional cohort; 6 subjects will receive 200 mg KM-819 and 2 subjects will receive placebo.

Table 1 Dose Groups for Part A

[figure not shown]
KM-819 Dose (mg)	Subjects on KM-819 (n)	Subjects on Placebo (n)	Total Subjects in Group (n)	Age Group
10†	6	2	8	Young adult male subjects
30†	6	2	8	
100†	6	2	8	
200†	6	2	8	
400†	6	2	8	
200	6	2	8	Elderly male or post-menopausal female subjects

† Doses between the current planned range may be assigned or a dose may be repeated depending on safety, tolerability, and pharmacokinetic data from previous subjects and cohorts.

All subjects will undergo a Screening period of up to 28 days and a 3-day Confinement period when they are hospitalized for study activities (Day -1 to Day 3). Subjects are required to return for outpatient visits on Day 4, Day 7, and for Follow-up Visit on Day 14.

PAREXEL International
Statistical Analysis Plan

Figure 1 Part A SAD study design

Part B, Multiple Ascending Dose (MAD):

This part includes up to 4 cohorts of healthy young adult male subjects receiving multiple ascending doses (MAD)s of KM-819, and 1 additional multiple-dose cohort of elderly male or post-menopausal female subjects.

It includes Up to 32 healthy young adult male subjects and 8 healthy elderly male or post-menopausal female subjects will be enrolled and randomized to receive either KM-819 or placebo. Each of the 4 dose escalation cohorts will consist of 8 healthy young adult male subjects; 6 subjects will receive 30 mg (3 x 10 mg tablet), 100 mg (1 x 100 mg tablet), 200 mg (2 x 100 mg tablet), or 400 mg (4 x 100 mg tablet) of KM-819 once a day (QD) for 7 days and 2 subjects will receive placebo. Cohorts will be dosed sequentially with escalating doses.

After completion of the 4 dose escalation cohorts, 8 elderly male or post-menopausal female subjects will be enrolled into an additional cohort; 6 subjects will receive KM-819 at a dose level not exceeding the highest dose tested in the young adult male cohorts and 2 subjects will receive placebo. The dose level will be decided by Investigator and Sponsor.

PAREXEL International
Statistical Analysis Plan

[figure not shown]
Table 2 Dose Groups for Part B

KM-819 Dose (mg)	Subjects on KM-819 (n)	Subjects on Placebo (n)	Total Subjects in Group (n)	Age Group
30†	6	2	8	Young adult male subjects
100†	6	2	8	
200†	6	2	8	
400†	6	2	8	
200	6	2	8	Elderly male or post-menopausal female subjects

† Doses between the current planned range may be assigned depending on safety, tolerability, and pharmacokinetic data from previous subjects and cohorts.

All subjects will undergo a Screening period of up to 28 days and an 8-day Confinement period when they are hospitalized for study activities (Day -1 to Day 8). Subjects are required to return for a Follow-up Visit on Day 14.

Figure 3 Part B MAD study design

*: Baseline
**: Randomization and study drug administration
#: Study drug administration

PAREXEL International
Statistical Analysis Plan

Criteria for Evaluation of the Study

The study involves safety, PK, and PD assessments. The specific endpoints are listed below.

• Safety Endpoints

Parts A and B:

1. Reporting AEs (nature, frequency, severity, time of onset/offset)
2. Standard clinical laboratory evaluations
3. Vital signs measurements (tympanic temperature, supine pulse, and supine BP)
4. 12-lead ECGs

• Pharmacokinetic Endpoints

Plasma PK parameters for KM-819 include the following for single dose and/or multiple dose analysis as appropriate:

Single Dose, Day 1 of multiple doses:

1. AUC(0-24): area under the plasma concentration-time from predose (time 0) to 24hrs post dose
2. AUClast: area under the plasma concentration-time from predose (time 0) to the last quantifiable concentration
3. AUCinf: area under the plasma concentration-time curve from predose (time 0) extrapolated to infinity
4. AUCinf (%extrap): Percentage of AUCinf that is due to extrapolation beyond tlast (%AUCex)
5. CL/F: apparent oral clearance
6. Cmax: maximum plasma concentration determined directly from the concentration-time profile
7. λ_z : terminal elimination rate constant
8. $t_{1/2}$: apparent terminal elimination half-life
9. tlag: lag time
10. tmax: time to achieve maximum observed plasma concentration determined directly from the concentration-time profile
11. Vz/F: volume of distribution

Kainos Medicine, Inc.

KMCP-819-K101

Final 1.0

14/Nov/2017

TP-EP.BS-WW-001-05

Effective date: 29 Jul 15

Related to: SOP-EP.BS-WW-002

Page 15 of 61

PAREXEL International
Statistical Analysis Plan

12. Other parameters, as appropriate, including dose-adjusted parameters (AUC_D_obs, AUClast_D, Cmax_D).

Day 7 of multiple doses:

1. AUCtau: area under the plasma concentration-time curve for a dosing interval
2. AUClast: area under the plasma concentration-time from predose (time 0) to the last quantifiable concentration
3. CL/F: apparent oral clearance
4. Cmax: maximum plasma concentration determined directly from the concentration-time profile
5. Cmin: minimum plasma concentration determined directly from the concentration-time profile
6. Ctrough: observed plasma concentration before dosing
7. Rac (AUC): observed accumulation by AUC
8. Rac (Cmax): observed accumulation by Cmax
9. tlag: lag time
10. tmax: time to achieve maximum observed plasma concentration determined directly from the concentration-time profile
11. Vz/F: volume of distribution
12. Other parameters, as appropriate, including dose-adjusted parameters (AUCtau_D, AUClast_D, Cmax_D).

Cerebrospinal fluid (CSF) PK parameter for KM-819 includes the following after multiple dose CSF sample collection:

1. KM-819 concentration in CSF

• **Pharmacodynamic Endpoints**

In both Parts A and B, mean and absolute value change from baseline at each post-baseline measurements for:

1. Bond and Lader Visual Analogue Scale (VAS)

PAREXEL International
Statistical Analysis Plan

2. Profile of Mood States (POMS)
3. Korean Wechsler Adult Intelligence Scale-IV (K-WAIS-IV)
4. C-SSRS

In Part B only, PD parameters in plasma and CSF including:

1. alpha synuclein oligomer
2. total Tau
3. phospho-Tau
4. Ratio of CSF concentration/Plasma Cmax

3. STUDY POPULATION

The study population will consist of for Parts A up to 40 and for Part B up to 32 healthy young adult male (19 to 45 years old) or healthy elderly male or post-menopausal female (over 60 years old). subjects.

For further details of inclusion and exclusion criteria please refer to the sections 4.1 and 4.2 of the CSP.

4. STATISTICAL BASIS FOR SAMPLE SIZE

It is planned to recruit in total 72 healthy young adult subjects and 16 healthy elderly subjects at one center in this study.

Part A: up to 40 healthy young adult male and 8 healthy elderly male or post-menopausal female subjects will be enrolled.

Part B: up to 32 healthy young adult male and 8 healthy elderly male or post-menopausal female subjects will be enrolled.

The sample size of 8 subjects each cohort in both parts is standard in first-in-human study for dose escalation. The number of subjects planned for both parts of this study is considered sufficient to achieve the study objectives (safety, tolerability, PK, and PD).

PAREXEL International
Statistical Analysis Plan

5. RANDOMIZATION

In each dose cohort, 8 subjects will be randomized to have 6 subjects receiving KM-819 and 2 subjects receiving placebo in both Part A and Part B.

For further details of randomization scheme please refer the section 4.5.2 and 4.5.3 of the CSP.

6. STATISTICAL ANALYSIS CONVENTIONS

6.1 Analysis Variables

6.1.1 Demographic and Background Variables

The following demography information will be collected at Visit 1:

- Date of informed consent
- Medical history (including previous and current medical conditions and medications)
- Age
- Sex
- Race
- Ethnicity

The following body measurements will be performed at Visit 1:

- Height (cm)
- Body weight (kg)
- Body mass index (BMI)

All medical history will be coded using Version **19.1** of the Medical Dictionary for Regulatory Activities (MedDRA).

PAREXEL International

Statistical Analysis Plan

6.1.2 Safety Variables

6.1.2.1 *Adverse Events*

An adverse event is any untoward medical occurrence that occurs in a subject or clinical investigation subject administered a pharmaceutical product, and which does not necessarily have to have a causal relationship with this treatment. An AE can therefore be any unfavorable and unintended sign (including abnormal laboratory finding), symptom, or disease temporally associated with the use of an investigational product, whether or not considered related to the product.

All AEs will be coded using the latest available version **19.1** of the Medical Dictionary for Regulatory Activities (MedDRA).

A treatment-emergent adverse event (TEAE) is defined as an AE that begins or that worsens in severity after at least one dose of the study drug has been administered.

Any AEs with incomplete start and end dates/times will be treated as follows:

- Adverse events with unknown start and/or end times (but where the date is known) will be imputed with a time of 00:00 h for the tabulations but will be shown as NK:NK in the listings (where NK = Not Known).
- Adverse events with completely unknown start dates will be considered as treatment-emergent for the tabulations and will be shown as NK in the listings.

6.1.2.2 *Clinical Laboratory Tests*

The following safety laboratory parameters will be measured at the time points mentioned in the table of assessments in the CSP section 7.

- **Clinical chemistry:** albumin, creatinine, glucose, urea, uric acid, TBIL, total protein, triglycerides (TG), total cholesterol, low-density lipoprotein (LDL) cholesterol, and high-density lipoprotein (HDL) cholesterol.
- **Hematology:** erythrocytes, mean corpuscular volume (MCV), mean corpuscular hemoglobin (MCH), neutrophils, eosinophils, basophils, lymphocytes, monocytes, platelets, leukocytes, hemoglobin, and hematocrit.
- **Urinalysis:** pH, protein, glucose, ketone, bilirubin, blood, and nitrite.

PAREXEL International
Statistical Analysis Plan

- **Serological marker:** Hepatitis B surface antigen (HbsAg), Anti-Hepatitis A Virus Immunoglobulin M (HAV IgM), Anti-Hepatitis C Virus (HCV Ab) and Anti-Human immunodeficiency virus (HIV Ab).
- **Urine Drug and cotinine screening, alcohol breath test:** Amphetamines, Barbiturates, Benzodiazepines, Cannabinoids, Cocaine, Opiates, Cotinine, and Alcohol.
- **Electrolytes:** sodium, potassium, calcium, and chloride.
- **Liver enzymes:** alkaline phosphatase (ALP), aspartate aminotransferase (AST), alanine aminotransferase (ALT), and gamma-glutamyl transpeptidase (GGT).

Clinical significance of out-of-range laboratory findings is to be determined and documented by the Investigator/sub-Investigator who is a qualified physician. Clinically relevant changes will be recorded as AEs in the eCRF (see Section 6.4.1.2 of CSP).

For safety laboratory tests, the total volume of blood drawn will be approximately 51 mL for subject in Part A SAD, and approximately 51 mL for subject in Part B MAD. Additional safety samples may be collected if clinically indicated at the discretion of the investigator.

6.1.2.3 *Vital Signs*

The following vital signs measurements will be obtained at the time points mentioned in the table of assessments in the CSP section 7 (Table 7-1 and Table 7-3).

- Blood Pressure (BP), supine (systolic and diastolic; mmHg)
- Pulse, supine (beats per minute)
- Body temperature (°C) (tympanic)

BP and pulse will be measured using the normal practice at study center; after the subject has been in a supine position for at least 5 minutes.

6.1.2.4 *Electrocardiograms*

The following electrocardiogram (ECG) parameters will be recorded at the time points mentioned in the table of assessments in the CSP section 7 (Table 7-1 to Table 7-3).

ECG will be performed using an internationally recognized 12-lead cardiograph (10 sec. rhythm strip) after the subject has been resting in a supine position for 5 minutes. All records will be done in

PAREXEL International

Statistical Analysis Plan

triplicate within 5 minutes, with at least a 1-minute interval. ECG printouts will include: date, time, at least 2-3 complexes for 12 leads data,

- Heart rate (HR) (beats per minute [bpm])
- QRS-duration (msec)
- PR (PQ)-interval (msec)
- RR-interval (msec)
- QT-interval (msec)
- QTcF (QT interval corrected for HR according to Fridericia) (msec)

Where QTcF is calculated using $QTcF = QT \times R-R^{1/3}$

The review of the ECG must be done by the Investigator or delegate. The interpretation of the ECG result must follow the categories: “normal”, “abnormal, not clinically significant”, or “abnormal, clinically significant”. Clinically significant findings must be recorded as AEs, or if present at Screening, it should be documented as concomitant illness (see Section 6.4.1 of CSP).

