### 8.2.1 Missing Data

Missing dates/times in AE and concomitant medication data will be handled as described in the SAP. There will be no imputation schemes applied to missing PK and/or PD data. Values that are below the limit of quantification (BLQ) in the PK data will be handled as described in the SAP.

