6.3.4 Missing Data

Any AEs with unknown severity or causality will be considered as ‘severe’ and ‘related’ respectively, for the tabulations. The unknown severity or causality without imputation will be presented in listings.

AEs with missing dates/times will be handled as described below. The incomplete dates/times without imputation will be presented in listings.

Concomitant medications (CMs) with missing times will be handled as described below. The incomplete times without imputation will be presented in listings.

All other data will be analyzed and reported as observed. No imputation schemes for other missing values will be applied.

PAREXEL International
Statistical Analysis Plan

Handling of AEs with Missing Dates/Times

Any AEs with incomplete start and or end dates/times will be handled as described below for the classification as treatment-emergent, assignment to treatment periods and calculation of duration.

- Adverse events with unknown start times, but with start date known, will be imputed with a time of 00:00 hours, unless the start date corresponds to any given dosing date, in this case the start time will be imputed with the time of dosing. If this results in a start date/time after end date/time of the AE then the start time will also be imputed with 00:00 hours.
- Adverse events with completely unknown start dates will be imputed with the date and time of first IMP administration, unless the end date is known and prior to first administration of IMP, then the start date will be imputed as the date of screening and a time of 00:00 hours.
- Adverse events with completely unknown end times, will be imputed with an end time of 23:59 hours;
- Adverse events with completely unknown end dates will be imputed with the date of final FU (or date of discontinuation in the case of withdrawals).

Adverse events with partially known start dates will be treated as follows:

- If only the day is missing, then the day will be imputed with the first day of the month, unless the month and year in which the AE started is a month and year in which IMP was administered, then the day will be imputed with the first day on which IMP was administered in that month. If this results in a start date after end date then the day will be imputed with the first day of the month.

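### SAP 6.1.2.1 and SAP 6.3.4 impute missing AE times differently and neither is given precedence, so a Day 1 AE with no recorded start time could be left out of the TEAE tables

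*SAP*

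**What the plan says.** SAP 6.1.2.1 (Adverse Events) defines a TEAE as "an AE that begins or that worsens in severity after at least one dose of the study drug has been administered". Two bullets on incomplete dates and times follow directly:

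- An AE with a known date but an unknown start and/or end time "will be imputed with a time of 00:00 h for the tabulations"; the listings show the time as not known. Dosing days are not excepted.
- "Adverse events with completely unknown start dates will be considered as treatment-emergent for the tabulations". No exception is made for an event whose known end date is before the first dose.

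SAP 6.3.4 (Missing Data) gives a second set of rules, to be used "for the classification as treatment-emergent, assignment to treatment periods and calculation of duration":

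- An unknown start time on a known date is set to 00:00 "unless the start date corresponds to any given dosing date, in this case the start time will be imputed with the time of dosing". If that puts the start after the end of the AE, the start goes back to 00:00.
- An unknown end time is set to 23:59.
- "Adverse events with completely unknown start dates will be imputed with the date and time of first IMP administration". One exception moves the start to the screening date at 00:00 instead; its condition is worded "unless the end date is known and prior to first administration of IMP".
- When the day, or the day and month, of the start is missing, the date can be imputed to the first dosing day. No clock time is given for that imputed date.

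Neither section refers to the other. Protocol 8.2.1 does not settle the matter: "Missing dates/times in AE and concomitant medication data will be handled as described in the SAP".

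**The concern.** Safety and tolerability are the primary objective. Protocol 8.6.1 restricts the AE summary tables to TEAEs. All ten AE summary tables listed in SAP section 8 (14.3.1.1 to 14.3.1.5, one of each per part) are titled as TEAE tables. AEs are collected from consent, so pre-dose events are also in the database and the Day 1 split between before and after dosing has to be made.

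The 6.1.2.1 bullets read as operative. They sit directly under the TEAE definition, they are stated to apply to tabulations, and the second bullet itself decides treatment-emergence. A programmer working from 6.1.2.1 and one working from 6.3.4 could produce different TEAE counts from the same data, and the SAP would not say which was correct.

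**Working it through.** There is no figure in the plan to reproduce. The check applies each rule as written to an AE with a known start date and an unknown start time.

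**Inputs.** Study drug is given from 8:00 to 10:00 (Protocol 7.2.2.1 for Part A, 7.2.3.1 for Part B). Part A has one dose, on Day 1; Part B has daily doses on Days 1 to 7. Each cohort has 6 active and 2 placebo subjects (Protocol 4.5.2).

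**Start times.** Imputed onset relative to first dose = imputed clock time minus dosing time. For Day 1:

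- 6.1.2.1: 00:00 − 08:00 = −8 h, to 00:00 − 10:00 = −10 h.
- 6.3.4: dosing time − dosing time = 0 h.

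| Start day | 6.1.2.1 | 6.3.4 | TEAE status differs? |
|---|---|---|---|
| Day −1 | 00:00, before first dose | 00:00, before first dose | No |
| Day 1, both parts | 00:00, 8 to 10 h before first dose | Time of first dose | Yes |
| Days 2 and 7, Part A | 00:00, after first dose | 00:00, after first dose | No |
| Days 2 and 7, Part B | 00:00, after first dose | Time of that day's dose | No; only the clock time differs |

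Status changes only on Day 1. Under 6.1.2.1 the event is then not a TEAE unless it worsens after dosing, which would bring it back under the definition.

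**End times.** Take an AE that starts and ends on Day 1 with both times unknown.

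- 6.3.4 alone: start 08:00 to 10:00, end 23:59. The start precedes the end and the dosing-time onset is kept.
- 6.3.4 start rule with the 6.1.2.1 end rule: start 08:00 to 10:00, end 00:00. The start is after the end, so the 6.3.4 fallback resets the start to 00:00, which is 8 to 10 h before dosing. The event is lost again.

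So adopting the 6.3.4 start rule does not protect such an event if the 6.1.2.1 end rule remains in force.

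**Unknown start dates.** For an AE with a completely unknown start date and a known end date before first dosing, 6.1.2.1 says treatment-emergent. Section 6.3.4 dates its start to screening, so it is not treatment-emergent. The TEAE definition agrees with 6.3.4 here.

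**Size per event.** If the affected event is a subject's only TEAE, or the only one in a given table row, incidence changes by 1/6 = 16.7 percentage points in a full active cohort. For placebo, if all planned cohorts of a part are run and pooled, the denominators are 6 × 2 = 12 in Part A and 5 × 2 = 10 in Part B. That gives 1/12 = 8.3 and 1/10 = 10.0 points.

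**The case against.** The strongest reply is that normal reading largely resolves the conflict. Section 6.3.4 is the dedicated missing-data section and names treatment-emergent classification as its purpose. The 00:00 bullet in 6.1.2.1 sits under analysis variables and does not mention classification. That is a fair account of what the authors probably meant. It does not remove the conflict, because 6.1.2.1 claims the tabulations and the tabulations are TEAE tables.

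The practical mitigation also stands. Subjects are confined on Day 1 and the onset time is a required item (Protocol 6.4.1.4). Missing data are discussed with the Investigator (Protocol 9.2), and queries are resolved before the overall code is broken (Protocol 5.5). SAP 6.3.15.1 plans a listing of all AEs, separate listings of SAEs and of withdrawals due to AEs, and a summary of any SAEs.

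A reader might infer three stronger points that the documents do not support:

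- **That 6.3.4 fails on its own terms**, because it puts onset at dosing while the definition says after a dose. The dosing-day substitution is made expressly for TEAE classification. On Day 1 it would serve no classification purpose unless onset at dosing counted. Saying so explicitly is tidy drafting.
- **That events with completely unknown start dates could be lost in the same way.** The second bullet of 6.1.2.1 counts them as treatment-emergent. The fault in that bullet runs the other way: it also takes in events known to have ended before dosing.
- **That dose escalation or stopping could be affected.** The criteria in Protocol 3.4 and 3.5 do not use the SAP's TEAE classification.

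**Conclusion.** The inconsistency is real and checkable in the text, for both start and end times. Its consequence is conditional. A Day 1 AE with no start time drops out of the TEAE tables only if 6.1.2.1 is programmed, or if its end rule is combined with the 6.3.4 start rule for an event ending the same day, and only if the event does not worsen after dosing. The documents do not support saying that the planned tables will omit such events, since 6.3.4 is the natural governing rule.

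The number of affected events is unknown and probably very small. The 16.7-point figure is nominal: it assumes a full cohort of 6 active subjects with no replacements, and an event that is the subject's only TEAE. The placebo figures also assume pooling across every cohort of a part, elderly included, which SAP 6.3.1 does not clearly state. No hypothesis test on AEs is planned. This is a low-priority correction, worth making because it costs little and concerns tables that report the primary objective.

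**What to change.** In SAP 6.1.2.1, delete the 00:00 imputation for both start and end times, keep the not-known display in the listings, and replace the blanket rule for unknown start dates. Suggested wording:

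> Incomplete AE start or end dates and times are handled under Section 6.3.4, which is the single operative rule for treatment-emergence, period assignment and duration. An AE with a completely unknown start date counts as treatment-emergent unless its known end precedes first dosing. Listings show unknown times as NK:NK and unknown dates as NK.

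Add to SAP 6.3.4:

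> An AE whose onset is imputed to the time of first dosing, or to the first dosing day from a partial date with no clock time, counts as treatment-emergent unless its known end precedes first dosing.

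The second sentence is needed because 6.3.4 gives no clock time for partial dates imputed to the first dosing day, so making it the single rule would otherwise leave those events open.

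The cost is SAP wording only, with a check that the AE derivation program follows 6.3.4 for start and end times. Data collection and study conduct do not change. The edit belongs in a SAP update before database lock; after lock it would go in a SAP Addendum, as the SAP's introduction provides.
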